1 INTRODUCTION

1.1 OVERVIEW

This is the protocol for a single-arm, prospective observational study concerned with the feasibility and acceptability of a newly implemented community pharmacy model to treat HCV for persons who inject drugs who historically have faced many barriers to care within conventional healthcare systems.

1.2 BACKGROUND

Opioid use disorder (OUD) and related health problems have emerged as a national health crisis. In 2017, an estimated 1.7 million American adults had a pharmaceutical opioid use disorder (OUD), and 0.7 million had a heroin-involved OUD.(1) The increase in opioid abuse and injection drug use (IDU) has led to a rise in overdose deaths(2) and new cases of HIV and hepatitis C virus infection (HCV).(3, 4) Injection drug use is the primary mode of transmission for HCV infection in the U.S.(5-7) After more than a decade of decline, the incidence of HCV is again on the rise, particularly among young adults, (8, 9) and in rural areas.(10) The recent outbreak in rural Indiana is also a stark reminder of the ever-present risk for HIV associated with IDU. (4)

We are at a unique historical moment, as we possess effective medications that can improve and sustain the lives of people who inject drugs (PWID). Currently there are medications that can be prescribed to 1) cure HCV (directly-acting antivirals), 2) prevent HIV infection (Pre-exposure Prophylaxis [PrEP]) and treat/prevent overdose (naloxone and medications to treat OUD). Furthermore, there is an unprecedented opportunity to eliminate HCV, a disease that affects the majority of PWID and causes substantial morbidity and mortality.(11) With the introduction of new directly-acting antiviral (DAA) medications, nearly all patients with HCV can be cured with 2–3 months of oral medications with minimal side effects. Expanding HCV treatment to populations at risk can reduce incidence and prevalence over time(12) (a concept known as “treatment as prevention”) and as such, the World Health Organization has proposed an ambitious goal to eliminate HCV by 2030.(13) Unfortunately, there is a translational gap in the delivery of these medications to PWID. Prior studies, including our own, show that <10% of PWID have been successfully treated.(14-16) While models of HCV care integrated in addiction treatment have been successful,(17, 18) many PWID lack access. Moreover, there are still major gaps in access to naloxone and PrEP among PWID.(19-22)

A community-pharmacy model has the potential to expand health services delivery and provide comprehensive, patient-centered care to PWID. For decades, pharmacists have been utilized in clinic and hospital settings to assist with management of acute and chronic diseases.(23, 24) Many successful specialty clinics that treat HCV currently depend heavily on the services of pharmacists. Pharmacists have extensive clinical training and highly developed expertise in pharmacotherapy, which makes them ideally suited for the management of HCV. Through the mechanism of Collaborative Drug Therapy Agreements (CDTAs), pharmacists are granted the authority to autonomously perform tasks related to medication management in collaboration with the practitioner through detailed protocols.(25) Restrictions on these designated services vary from state to state but can include all aspects of

medication management from testing and counseling to prescribing and dispensing medication.(26) Kelley-Ross, our community-pharmacy partner, in 2012 successfully implemented a take-home naloxone program for persons at risk for opioid overdose(68) and more recently started a program for providing PrEP (“One-Step PrEP”),(27) which enables persons to receive all services (screening, counseling, prescribing, dispensing, and follow-up) at their pharmacy site.

The HepPSI Study builds upon the existing Kelley-Ross PrEP clinic platform to offer a comprehensive package for HCV treatment that would also include access to naloxone and PrEP on-site, as well as linkages to low-threshold opioid treatment programs that provide buprenorphine or methadone. During Phase 1 of this research, we conducted qualitative interviews with people who inject drugs living with hepatitis C regarding motivators, barriers, and preferences for HCV treatment. Phase 1 findings have since been used to inform the development of the community-pharmacy program (One-Step Hep C Free) that will be piloted in this Phase 2 research.

2 STUDY OBJECTIVE

Single-arm, prospective observational study of 40 adult persons who inject drugs (PWID) who screen positive for hepatitis C virus (HCV) with a reactive antibody test at community sites who are offered facilitated linkage to community-pharmacy program through patient navigators. Individuals who are eligible and enroll will complete a baseline survey to assess sociodemographics, substance use, HIV risk behaviors, and awareness of and interest in HCV treatment. After the survey, the participants will be linked to the community-pharmacy program, via the patient navigator, where treatment for HCV and opioid use disorder (OUD), as well as pre-exposure prophylaxis (PrEP), Naloxone and vaccinations, will be offered to participants.

After 6 months, participants will complete a follow-up survey, which will include questions on: whether an evaluation for HCV occurred at the community pharmacy or elsewhere, whether HCV treatment was initiated since baseline visit and whether cure was achieved, substance use, HIV risk behaviors, receipt of medications for opioid use disorder, Naloxone and PrEP receipt, medication adherence, and information on injecting networks.

3 STUDY DESIGN

3.1 OVERALL DESIGN

Forty participants will complete two study visits during this time. After screening and enrollment at a community site, participants will complete a Baseline Survey. Upon completion of the Baseline Visit, participants will either be connected to a patient navigator responsible for linking the participants to the community-pharmacist OR referred directly to the community-pharmacist if on site. Six months after the initial Baseline Visit, participants will be contacted to complete a final Follow-up Survey.

[figure not shown]
3.1.1 COMPENSATION

Participants will be compensated for their time and may receive up to \$80. Payment for visits will differ as follows:

- \$30 reimbursement for the completion of Baseline Survey
- \$50 reimbursement for the completion of Follow-up Survey

3.1.2 STUDY SCHEMA

Study Participant Flow

*For individuals who have SVR12 data missing at 6-month visit, additional chart reviews will occur up to 3 months after SVR12.

3.2 ELIGIBILITY

3.2.1 INCLUSION CRITERIA

1. ≥ 18 years old
2. Reports injecting drugs within 90 days of screening
3. Positive HCV test documented (screening antibody test or viral load test)
4. Not currently taking medications to treat HCV, and never previously treated with direct-acting antivirals (DAAs) for HCV
5. Willing to undergo evaluation for HCV through a community pharmacy program and work with Patient Navigators
6. Provides release of information ("ROI") to access community pharmacy program records and/or other HCV treatment providers

3.2.2 EXCLUSION CRITERIA

1. People who plan to leave the Seattle area within 6 months
2. Who do not wish to be treated for their HCV infection
3. Who are known to be pregnant
4. Who report impending incarceration that would disrupt clinical care
5. Who are not comfortable reading and speaking English

At researcher's discretion, participants may be excluded if their behavior poses safety concerns for research staff or other participants.

3.3 RECRUITMENT AND RETENTION STRATEGIES

3.3.1 RECRUITMENT STRATEGY

Subjects will be recruited through (1) syringe services programs (including the Downtown Needle Exchange at Robert Clewis Center) (2) opioid treatment and behavioral health programs (including Evergreen Treatment Services) (3) community-based agencies that serve persons who inject drugs living with HCV (including the Hepatitis Education Project), and (4) low-income housing sites/homeless shelters. We will also recruit participants from the Phase 1 qualitative study who gave permission to be contacted in the future to participate in this new study.

The uncertainty of the COVID-19 response's impact has led us to develop multiple recruitment plans:

1. Research staff may receive referrals to the study from personnel who interact with potential subjects at these sites.
2. Potential participants may self-refer to the study by contacting Research staff directly using information on public recruitment materials.
3. If research staff are able to go to sites listed above for recruitment, they will approach potential subjects directly.

We will primarily rely on staff at the community sites listed above to make referrals to study staff members and will keep signage and flyers on-site at these locations with our recruitment times at a given site. When appropriate, we may directly approach potential participants at these sites. Prior to conducting eligibility screening visits in person at these agencies, staff will identify a physical space at a given agency that will allow staff to maintain confidentiality.

3.3.2 RETENTION STRATEGY

During the consent process, study staff will collect the participant's contact information (HepPSI Participant Locator Form, Appendix 8.1). Participants consent to providing additional contacts in case a

study staff person is unable to reach the study participant. Forms have space for up to four additional contacts. The study staff person collecting this information will inform the participant, again, that these individuals will only be contacted if they themselves cannot be reached. This form will be stored in a locked filing cabinet with the research team and should never be stored with participant study data. This information will be entered into the HepPSI Phase 2 Participant Tracking Database project on REDCap under the form “Participant Contact Information”.

Research staff will contact participants every 2 months to ensure contact information is up to date and to check-in. Staff will utilize Patient Navigator to stay connected with participants when possible. Each time contact with a participant is made, that instance will be documented in the HepPSI Phase 2 Participant Tracking Database project on REDCap under the form “Contact Log”.

For further information regarding HepPSI Phase 2 Participant Tracking via REDCap, refer to the **HepPSI Phase 2 REDCap Manual of Procedures**.

3.3.3 PATIENT NAVIGATOR RESPONSIBILITIES

Primary

1. Facilitated linkage to community-pharmacy program
2. Outreach at syringe exchange programs, addiction treatment programs, homeless shelters, and advocacy groups for individuals who may be eligible for the community-pharmacy program

Secondary

1. Maintain contact with participants throughout treatment; facilitated by medical case management intake (see section 8.4)
2. Refer interested participants to other resources (including linkages to existing “low-threshold” programs that offer OUD medications in close proximity)

3.4 STUDY SITES

3.4.1 HEPATITIS EDUCATION PROJECT

The Hepatitis Education Project (HEP) is an advocacy group that provides numerous services for persons with HCV, including medical case management, Hepatitis B and C screening, a syringe access program, and more. Participants will be recruited from the various community sites where the Hepatitis Education Project currently offers HCV screening. This includes local syringe exchange programs, opioid treatment programs, homeless and urban drop-in shelters, low income housing units, and the main HEP office near downtown Seattle*.

Community Pharmacists will be onsite at the main HEP office during their syringe service program hours (Thursdays 1-5pm, as of 11/05/2020).

*11/05/2020 – as a result of the COVID-19 Pandemic, HEP has limited their outreach services and general operations. Their syringe service program will be located outdoors in a lot adjacent to the main HEP office.

3.4.2 EVERGREEN TREATMENT SERVICES/ DOWNTOWN EMERGENCY SERVICE CENTER

Evergreen Treatment Services (ETS) is an opioid treatment program organization with three locations in the Puget Sound region. Study recruitment will be focused at the Seattle Clinic site where ETS patient attend medical provider appointments, counseling services, and receive their medications for opioid use disorder (MOUD). ETS medical providers and counselors can refer their patients for HCV treatment to the Community Pharmacists and Patient Navigator when both are located at the ETS Seattle Clinic one morning a week, or directly to the Kelley-Ross pharmacy/HEP locations. Community Pharmacists and Patient Navigator will be onsite at the Seattle Clinic on Thursdays mornings 9am-12pm, as of 03/04/2021.

Downtown Emergency Service Center (DESC) provides supportive housing, case management, substance use disorder treatment, and medical services at 12 locations throughout Seattle and several other adjacent cities. DESC providers at several locations are able to refer clients interested to HCV care to the Community Pharmacists for treatment. However, given the limited space available at DESC locations, DESC clients who are interested in participating in the study would need to travel to HEP so that research staff could screen for eligibility and complete consent procedures.

4 STUDY ASSESSMENTS AND PROCEDURES

4.1 SCREENING

Staff at community sites will be educated about the study and asked to refer interested individuals who may be eligible. If research staff are onsite, community site staff will “hand off” potential participants to speak with research staff directly. Otherwise, interested individuals will be referred or self-refer to research staff via phone or email. Once connected to interested individuals, the trained research staff will explain the study and screen them in a private space on site or over the phone (See IRB-approved Screening Script, Appendix 8.2). Each screened subject will receive a unique screening ID (YXXX) that will be documented in a protected spreadsheet, along with the results of the screening encounter.

4.1.1 DETERMINING ELIGIBILITY

A REDCap Screener assessment has been designed to notify the assessor when a subject meets all inclusion criteria and is considered eligible. If an eligible subject is uninterested in participating, the

assessor should document the reason on REDCap. Please refer to the **HepPSI Phase 2 REDCap Manual of Procedures** for further information and procedures when eligibility has been determined.

If time allows, consenting, enrollment, and the baseline visit will follow the screening visit on the same day.

4.1.2 DATA COLLECTED DURING SCREENING

Data collected during screening will be captured in REDCap. This data includes the subject's date of birth, basic demographic information, any major comorbidities that would preclude treatment through the community-pharmacy program, and other items related to determining whether the subject meets inclusion criteria. The screener form is coded in REDCap to automatically notify the assessor on whether the subject is eligible or ineligible to participate in the study.

No personal identifying information will be entered into the REDCap Phase 2 Screener Project.

4.2 ENROLLMENT PROCEDURES

Once deemed eligible to participate in the study, study staff will facilitate enrollment procedures, beginning with informed consent after which subjects will confirm their intent to continue the enrollment process. During the enrollment process, participants will also consent to provide contact and alternate contact information for tracking purposes (See Retention Strategies). At the end of the enrollment process, participants will be assigned a unique Study ID (40XX).

4.2.1 INFORMED CONSENT

Consent will be obtained by trained research staff from patients who meet all inclusion criteria. The PI will not consent patients. The process of consenting participants will occur in a private space. The study will be described and the potential subject will be asked if they have any questions about the study procedures. If the individual agrees to participate after consideration of all options, they will provide written consent.

The research staff will give the subjects adequate time to look at and read the informed consent form, summarize each section and ask the subjects if they understand and if they have any questions about the study procedure. As part of the informed consent, the research staff may assess the subjects' understanding of the information presented during the consent process. This may include having the subject articulate their understanding of the study purpose, procedures, risks, etc.

After reading through informed the consent form, subjects who agree to participate will sign two copies. One copy will be sent home with the participant and the other will be stored in a locked cabinet with the research study team. This form should never be stored with participant study data.

4.2.1.1 HIPAA AUTHORIZATION AND RELEASE OF INFORMATION FORMS

4.2.1.1.1 HIPAA AUTHORIZATION FORM

The University of Washington IRB office has been contacted to obtain an organization specific HIPAA Authorization template, and study staff made necessary changes to the template to meet study needs. Study staff must have the study participant complete and sign two HIPAA Authorization Forms. One form will be given to the participant and the other will be stored in a locked filing cabinet with the research team. This form should never be stored with participant study data.

4.2.1.1.2 RELEASE OF INFORMATION FORMS

Participants will be asked to sign Release of Information (ROI) forms that allow study staff to disclose medical information relevant to the study. Medical information may include sexually transmitted disease, acquired immunodeficiency syndrome (AIDS), or human immunodeficiency virus (HIV). Participant's health records may also include sensitive information about behavioral or mental health services and treatment for alcohol and drug abuse

Upon enrolling in the study, participants will sign two ROI forms permitting disclosure of medical information: one for Hepatitis Education Project, and one for Kelley-Ross Pharmacy.

4.3 STUDY VISITS

Participants will be enrolled and complete the baseline assessment at study start. Over the course of the study, two total assessments will be conducted: one at baseline visit (study start) and one at final visit (six months post-study start date). Study visits will take place in-person at Hepatitis Education Project or other community sites hosting HEP services. Due to the COVID-19 pandemic, study staff are prepared to transition to remote visits if need be. After the baseline study visit, participants will receive a \$30 reimbursement, and then they will be linked to a HEP Patient Navigator who will facilitate their connection to the community pharmacy program. After the final study visit, participants will receive a \$50 reimbursement.

Assessment data will be collected primarily on REDCap, but research staff completing research visits should have, at all times, IRB approved paper assessment copies in case of any technical difficulties with study laptop.

Besides having paper copies of all assessments, research staff will carry a small binder of Assessment Cards. These Assessment cards are response options to all assessment items in large printed font to assist participants during the assessments.

4.3.1 ASSESSMENTS OVERVIEW

The baseline survey will assess socio-demographics, substance use*, HIV risk behaviors*, and awareness of and interest in HCV treatment. After 6 months, participants will complete a follow-up (final) survey which will include information on:

- a) Whether an evaluation for HCV occurred at the community pharmacy or another site since the baseline visit
- b) Whether HCV treatment was initiated since baseline visit— assessed by self-report and pharmacy/medical records for confirmation.
- c) For patients who report that they have not been treated for HCV, reasons why (co-morbid conditions interfering, competing priorities, lack of interest, spontaneous clearance, etc.).
- d) Substance use*—measured by the modified Addiction Severity Index (ASI)(28)
- e) HIV Risk Behaviors*—measured by the modified HIV Risk Behaviors Survey (RBS)(29, 30)
- f) Receipt of naloxone, PrEP, and medications for OUD: self-report, confirmed with review of pharmacy record of dispensation/refills.
- g) Medication satisfaction, tailored to direct-acting antiviral treatment
- h) Medication adherence— assessed by record of medication pick-ups and also through self-report
- i) Injecting network (number of partners they have shared injected drugs with and, of those, how many they would be willing to refer to the site where they were treated)
- j) Completion of HCV Treatment – self-report and medical record chart review to assess if HCV treatment was fully completed.
- k) Sustain Virologic Response (SVR12) – Medical record review to assess obtainment of SVR12 results among participants who complete HCV treatment. For patients missing SVR12 results at the time of 6 month follow-up (either due to not yet having reached 12 post-treatment date or simply missing data), chart reviews will be conducted again up to 3 months after the 6 month follow-up.

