4.3.2 DATA COLLECTION TOOLS

The primary method of collecting data will be completed electronically through REDCap. REDCap is a web-based HIPAA compliant platform that will be used to collect and export participant data. Each participant will have a unique Study ID (40XX) that will be used to distinguish their REDCap records. Identifiable participant information will be kept separately from participant data. In instances where paper assessments are used, those documents will be stored in a locked cabinet at Harborview Medical Center, separated from any identifiable patient information as well. Study ID assignments and participant names will be tracked through a password-protected Excel spreadsheet that will be stored on a secure drive accessible to only study staff. This Excel spreadsheet will also document information regarding study visits, including start date, the projected final visit date, and actual final visit date, as well as any study withdrawal details.

Further information about REDCap can be found in the [HepPSI REDCap Manual of Procedures](#).

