4. Baseline and 6-month follow-up substance use in past 30 days via modified Addiction Severity Index (ASI)
5. Baseline and 6-month follow-up the number of injecting episodes using shared needle/syringe within the past 30 days via the modified Risk Behaviors Survey (RBS)
6. Baseline and 6-month follow-up the number of episodes of unprotected vaginal or anal sex within the past 30 days via RBS
7. Self-reported participant Likert scale surveys of satisfaction and willingness to refer an injecting partner to the community pharmacy for treatment
8. The number/percent who complete treatment for HCV, defined as having received all planned medication doses.
9. SVR12 defined as undetectable HCV viral load at least 12-weeks post treatment completion

NOTE: This analysis plan does not include the data on injection network

Inclusion/Exclusion Criteria: *Defines the population to be analyzed. Describe criteria that were part of original data collection and additional criteria needed for this particular project.*

Inclusion criteria:

1. Age ≥ 18 years old
2. Injected any drug within the past 90 days (intravenous or intramuscular)
3. Tested positive for HCV (screening and/or confirmatory viral load) at a community testing site (syringe exchange programs, addiction treatment programs, homeless shelters, urban drop-in shelters and low-income housing sites)
4. HCV treatment naïve and not currently already receiving treatment
5. Willing to undergo evaluation for HCV at a community pharmacy

Exclusion criteria:

1. People who plan to leave the Seattle area within 6 months
2. Do not wish to be treated for their HCV infection
3. Are known to be pregnant
4. Report impending incarceration that would disrupt clinical care
5. Are not comfortable reading and speaking English
6. Report being HIV-positive
7. Report having end-stage renal disease or require dialysis treatments
8. Report prior enrolled in (i.e. completed at least the initial intake appointment) the Kelley-Ross pharmacy program for hepatitis C treatment ("One Step Hep C Free")

Data and Variables Needed for Analysis

Add rows to tables as needed

If a dataset or variable needs to be created / does not exist yet, you can note that here.

Variable Name	Definition	Variable type	Sub-aim #
m6hcvtxpharmd	Since our first visit, were you seen by the pharmacist (refer to them by name) for hepatitis C medications?	Yes/no	1

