ehrtxkelleyross, ehrtxkrevaldoc (EHR)	Did this participant seek treatment through the KR community pharmacy program? (defined as presence of initial eval note by Kelley-Ross pharmacist)	Yes/no	1

Variable Name	Definition	Variable type	Sub-aim #
M6hcvpharmdmed	Since our first visit, did you take any medications to treat hepatitis C through the pharmacist ([name])? This can mean that you took only one pill, some of the pills, or all of the pills you were prescribed.	yes/no	2
M6hcvpharmdmedcom pno	If no, why not?	Check all that apply	2
M6hcvothpromed	Since our first visit, did you take any medications to treat hepatitis C through the provider ? This can mean that you took only one pill, some of the pills, or all of the pills you were prescribed.	Yes/no	2
ehrtxinitiate (EHR)	Was treatment initiated? (Defined as meds were prescribed, regardless of showing up to receive)	Yes/no	2
ehrtxwhynotinitiated (EHR)	Why was treatment not initiated? (Response options: ppt determined not appropriate for tx, ppt verbalized not wanting tx, ppt never returned, ppt did not complete workup, other (check all that apply))	categorical	2
M6hcvpharmdmedper cent	On a scale of 0% to 100%, how much of your medication did you take? Where taking every pill would be 100%, taking half the pills would be 50% and not taking any pills would be 0%. If you are still in your hepatitis C treatment course, think about how much of the medications you should have taken to date.	Integer, 0-100	8

M6hcvothpromedcom p	Have you completed your treatment regimen for hepatitis C(normally 8-12 weeks of daily medications)?	Yes/no	8
ehrtxiterrupt; ehrothxiterrupt (EHR)	Does the EHR text mention a treatment interruption?	Yes/no	8
ehrtxiterruptdays, ehrtxiterruptweek; ehrothxiterruptdays, ehrothxiterruptweek (EHR)	If yes, how many days? And at what week did the interruption occur?	Integer, -100, 1-12	8
ehrtxadherence (EHR)	Do the notes document non-adherence?	Yes/no	8
ehrtxdctx (EHR)	Did the provider pre-maturely discontinue treatment?	Yes/no	8
ehrrxreceived (EHR)	Did the participant ever pick-up/receive their medication from the pharmacist?	Yes/no	8
ehrrx1disptime (EHR)	Date of first medication dispensation	Date_mdy	8
ehrrx2actualdisptime (EHR)	Date of actual second medication dispensation	Date_mdy	8
ehrrx3actualdisptime (EHR)	Date of actual third medication dispensation	Date_mdy	8
m6hcvpharmdsrv12	Did you have a blood test to see if you were cured?	Yes/no	9

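### The protocol gives two different end dates for repeat SVR12 chart review, which agree only when treatment ends at about week 14

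*Protocol*

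**What the plan says.** Two places in the protocol deal with the same people, those whose SVR12 result is missing at the 6-month visit.

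- Section 4.3.1, item k: "chart reviews will be conducted again up to 3 months after the 6 month follow-up". It gives two reasons for a missing result: "either due to not yet having reached 12 post-treatment date or simply missing data". It seeks SVR12 results among participants who complete treatment.
- Section 3.1.2, footnote to the participant flow figure: "additional chart reviews will occur up to 3 months after SVR12".

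Sub-aim 9 of the SAP sets the timing of the endpoint: "SVR12 defined as undetectable HCV viral load at least 12-weeks post treatment completion". The SAP gives no closing date for collecting it. A self-report item in the SAP variable table describes the course as "normally 8-12 weeks of daily medications". Section 4.3 of the protocol puts the final visit six months after study start. No latest treatment start is set. The SAP's 6-month item on the percentage of medication taken has wording for people who are still on treatment at that visit. Section 6 lists SVR12/cure among the secondary outcomes.

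**The concern.** One closing date is fixed relative to baseline. The other moves with each participant's end of treatment. Neither document says which governs, so the results that reach the dataset depend on which page the staff follow. Neither rule is the longer one for everyone, so staff cannot simply default to the more generous.

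Item k also has a consequence of its own. Under it, whether a cure can be seen depends on how quickly a participant linked to the pharmacy and started treatment, which is part of what the pilot evaluates. What is at stake is the completeness of a secondary outcome in a 40-person study. The primary outcome, evaluation in the pharmacy program, and its confidence interval are not involved.

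**Working it through.** The plan states no figure for these windows, so there is none to reproduce. The check is timeline arithmetic.

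**Inputs**
- Final visit: 6 months, taken as week 26 and on time (section 4.3; no visit window is stated).
- Extension: 3 months, taken as 13 weeks (both passages).
- SVR12 due date: 12 weeks after treatment ends (SAP sub-aim 9).
- Course length: 8 to 12 weeks (SAP self-report item), uninterrupted.
- Footnote: with the result missing, 3 months after SVR12 is read as 3 months after its due date.

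**Formulas**, with *t* the week treatment ends
- Item k closes at 26 + 13 = week 39.
- The footnote closes at *t* + 12 + 13 = *t* + 25.
- They are equal when *t* + 25 = 39, so *t* = 14. SVR12 is then due at week 26, the 6-month visit itself.
- Time between the due date and closure under item k: 39 − (*t* + 12) = 27 − *t* weeks. Under the footnote it is always 13 weeks.

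| Treatment ends (week) | SVR12 due | Footnote closes | Item k closes | Footnote minus item k | Weeks left after due date, item k |
|---|---|---|---|---|---|
| 8 | 20 | 33 | 39 | −6 | 19 |
| 12 | 24 | 37 | 39 | −2 | 15 |
| 14 | 26 | 39 | 39 | 0 | 13 |
| 20 | 32 | 45 | 39 | +6 | 7 |
| 26 | 38 | 51 | 39 | +12 | 1 |
| 34 | 46 | 59 | 39 | +20 | none |
| 38 | 50 | 63 | 39 | +24 | none |

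The last two rows are starts at week 26 with an 8-week and a 12-week course.

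Week 14 also separates the two groups that item k names. People not yet at their 12-week date at the visit (*t* after 14) have the shorter window under item k. People already past it with no result (*t* before 14) have the shorter window under the footnote. The largest loss there, 6 weeks, is for an 8-week course begun at baseline.

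**Limit under item k.** An SVR12 can be captured only if *t* + 12 ≤ 39, so *t* ≤ 27.
- Someone who finishes on the day of the visit has 3 × 30.44 − 84 = 7.3 days between the due date and closure.
- Someone with more than about one week of treatment left at the visit has none.
- The latest start is 27 − 8 = week 19 for an 8-week course, or 27 − 12 = week 15 for a 12-week course.

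**Sensitivity**
- Calendar months (26.09 and 39.13 weeks) put the crossover at 14.09 and the latest starts at 19.13 and 15.13.
- Reading 6 months as 24 weeks and 3 months as 12 closes item k at week 36, puts the crossover at week 12 and the latest starts at 16 and 12, and leaves no margin for someone finishing at the visit (36 − 12 − 24 = 0).
- If the visit is held at week 30 and its actual date starts the clock, closure is week 43 and the latest starts are 23 and 19. The margin relative to the visit is still 13 − 12 = 1 week.

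**The case against.** The best defence is that item k is a coherent fixed window. It concerns completers, and anyone who has completed by an on-time 6-month visit reaches the SVR12 due date by week 38, inside the week-39 closure. The starters it cannot reach are all still on treatment at month 6, and not following them further is a legitimate choice of follow-up length in a small pilot. On this view the footnote is loose shorthand for item k, attached to a figure that the text does not reproduce. Taken literally it cannot apply to someone who has no SVR12.

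Much of this stands. The footnote's week numbers, and so the week-14 crossover, depend on reading it as the due date. The early finisher's loss is slight, since 13 weeks after the due date remain. A fixed window would be defensible if stated. But the protocol does not state that choice: item k is not expressly limited to people who have completed by the visit, and the footnote says something else about the same group. If the footnote is a slip, it still has to be corrected. The limits under item k do not depend on the footnote at all.

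It can also be said that aligning the footnote would be enough. That does remove the contradiction, and it is kept below as the fallback. The fuller rule adds only what the longer of the two existing passages already implies.

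**Conclusion.** The contradiction is real and in current text. With an on-time visit the two rules differ by 6 weeks in one direction for a week-8 finisher and by 12 weeks in the other for a week-26 finisher. Under item k, people with more than about a week of treatment remaining at the visit cannot contribute an SVR12 even if they complete. The documents give no distribution of start times, so the number affected is unknown and no share is estimated. The point is worth correcting, but it touches one secondary outcome only.

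Four stronger readings are tempting and are not supported.

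- *Item k loses SVR12 for people who complete by month 6.* It does not if the visit is on time, although the last finishers have only days.
- *The cure proportion is biased downward because initiation is counted from prescription* ("Defined as meds were prescribed, regardless of showing up to receive"). No SVR12 denominator is stated, and item k and sub-aim 9 both point to completers.
- *The start of the 3 months is undefined because the tracking file holds* "the projected final visit date, and actual final visit date". That passage only describes a spreadsheet. The natural reading of item k is the visit as held.
- *An end-of-treatment negative would be counted as SVR12.* The SAP lists neither a viral-load date nor a treatment-end date, but it sets the 12-week rule, lists dispensing dates and says "Add rows to tables as needed". Appendix 8.4 itself separates an undetectable load from cure. This is missing detail, not an error shown.

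**What to change.** State one rule in both sections 3.1.2 and 4.3.1. For participants who start treatment by the 6-month follow-up and go on to complete it, repeat chart review runs to the later of (a) 3 months after the 6-month follow-up and (b) 3 months after the SVR12 due date, as far as the signed releases allow. This shortens no one's window. If it is not feasible, align the footnote to item k.

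Either way, report completers, and those still on treatment, whose SVR12 is not yet due at the cut-off separately from those whose result is due but missing. State the denominator for SVR12.

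The cost is wording in two places, a few later chart reviews and a later data lock, with no new visits. Review would run to week 51 (11.7 months) for a week-26 finisher, and to week 59 or 63 (13.6 or 14.5 months) for a week-26 start on an 8- or 12-week course. Navigators already follow clients to the SVR12 result and ask for its date (Appendix 8.4, steps 11 to 13). Section 4.2.1.1.2 gives no duration for the releases, so check their term first. Listing the viral-load date in the SAP table, to apply the 12-week rule directly, is optional housekeeping.
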